5.4. Potential Benefits and Risks

5.4.1. Potential Benefits of Setrusumab

5.4.2. Potential Risks

To date in clinical trials, setrusumab has demonstrated an acceptable safety profile.

5.4.3. Benefit Risk Conclusion

Taking into account measures to minimize risk to subjects in this study (Section 5.5), the potential risks identified in association with setrusumab are justified by the anticipated benefits that may be afforded to subjects with OI.

5.5. Risk Minimization

[figure not shown]
This study has been carefully designed to minimize potential risks to subjects.

The study includes measures to monitor patients with an aim to minimize potential risks of setrusumab based on safety data from previous clinical studies with setrusumab as well as product class information from other anti-sclerostin antibodies.

The following potential risks will require reporting to permit processing as AESI for the study (refer to Appendix 4 for details on safety reporting).

Measures to minimize risk and monitor for AESIs are listed below.

Additional measures to monitor for other potential risks are listed below.

In addition to the above, the incidence, seriousness, severity, duration, and outcome of all potential risks will be regularly monitored throughout the study and follow up will be performed to obtain complete information on all reported events to enable a thorough medical assessment.

6. OBJECTIVES AND ENDPOINTS

Study objectives and endpoints are defined for each study period. Objectives and endpoints for the Observation, Retreatment, and Extension Periods are shown in Table 6, Table 7, and Table 8 respectively.

Table 6: Study Objectives and Endpoints for the Observation Period

[figure not shown]
[figure not shown]

Table 7: Study Objectives and Endpoints for the Retreatment Period

OBJECTIVES	ENDPOINTS
Primary	
Evaluate BMD after 12 months of retreatment with	Percentage change from Retreatment Baseline in lumbar
monthly setrusumab in adults with OI	spine BMD measured by DXA after 12 months of
•	setrusumab
Secondary	
Evaluate BMD during 12 months of retreatment	Percentage change from Retreatment Baseline in total hip
with monthly setrusumab in adults with OI	BMD measured by DXA at Month 12 of the Retreatment
···,	Period
Evaluate fractures after 12 months of retreatment	Annualized new fracture rate as confirmed by radiograph
with monthly setrusumab in adults with OI	during the Retreatment Period
Tertiary	during the red ettainent remod
CCI	
	-
	•
CCI	BMD, bone mineral density;
	DXA, dual-energy X-ray
absorptiometry; CCI	
	_

Table 8: Study Objectives and Endpoints for the Extension Period

During the Retreatment Screening Visit subjects undergo screening to confirm eligibility for retreatment with setrusumab, including an assessment of serum calcium and 25-OH-vitamin D (Section 8.2 and Section 8.5). If a Visit occurred within 4 weeks prior to the Retreatment Baseline, then safety laboratory tests do not need to be recollected at the Retreatment Screening Visit, except for the chemistry panel, which is collected at both the Retreatment Screening Visit and Retreatment Baseline.

The dosing strategy in the Retreatment and Extension Periods will be based on the pharmacokinetic (PK) and serum bone turnover markers from the Phase 2b ASTEROID study and the Phase 2 Period of the UX143-CL301 study. The selected dose will be in the range of 20 to 40 mg/kg CC

During the single-arm Retreatment Period, subjects receive open-label setrusumab QM for 12 months. During the Retreatment Period, subjects are assessed for safety and efficacy of

Following the Retreatment Period, subjects enter an Extension Period, in which they are randomized 1:1 to either continue treatment with open-label setrusumab QM or transition to open-label setrusumab CC for at least 12 months or until setrusumab is commercially available. For the Extension Period dosing groups, randomization will be stratified by OI type (I vs III/IV).

7.1.1. Number of Sites

Approximately 24 sites

7.1.2. Number of Subjects

Up to 112 subjects will be enrolled; only those who participated in ASTEROID.

7.1.3. Rationale for Study Design

The purpose of this study is to further investigate the safety and efficacy of setrusumab in adults with OI. The Phase 2b study (ASTEROID; MBPS205) demonstrated clinically meaningful, dose-dependent increases in BMD over the course of 12 months of setrusumab, with discontinuation of therapy resulting in partial loss of BMD gains over the next 12 months. The proposed study will re-recruit these subjects to monitor the long-term effects off-setrusumab and to evaluate the effect of setrusumab retreatment. The potential inclusion of up to 112 subjects treated with open-label setrusumab for up to 2 years will augment the current safety and efficacy database. These results will help inform longer-term treatment strategies in adults with OI, a chronic disease for which no therapy is currently approved globally. Additionally, retreating these adults with OI will provide insight into the effects of stopping and restarting treatment with setrusumab, potentially with and without interim bisphosphonate use, and help characterize long-term safety with setrusumab treatment.

The proposed study is divided into multiple parts which each have their own goal. During the Observation Period, data will be collected to evaluate setrusumab off-treatment effects. Additional data will be collected from the Off-Study Period via chart review to provide additional information on post-setrusumab effects that occurred prior to enrollment into the Observation Period. The Observation Period visits will occur at intervals relative to the Phase 2b study. The effects of initial setrusumab dose-level and zoledronic acid administration post-setrusumab will be further elucidated, with specific evaluation of changes in BMD and fracture rate over time. Together, data collected from the Off-Study and Observation Periods provide a long-term view of the effects of setrusumab discontinuation in adult OI.

The Retreatment Period will evaluate the efficacy and safety of 12 doses of open-label setrusumab QM. Retreatment may provide additional insights into the effects of setrusumab in subjects that previously received setrusumab. The potential impact of how subjects were treated in the original Phase 2b study (initial setrusumab dose-level and/or zoledronic acid

administration) will be further elucidated. Open-label use of monthly setrusumab is warranted based on the Phase 2b data that demonstrated the relative safety and efficacy of monthly dosing in these patients.

The Extension Period will extend setrusumab administration beyond 12 months to determine the longer-term safety and efficacy of retreatment in adults with OI. The Extension Period will also explore dosing strategies, QM or helping to optimize the treatment regimen for longer-term treatment with setrusumab. Demonstration of continued improvements in DXA BMD or other endpoints beyond 12 months may justify extended use of setrusumab in adult OI.

7.1.4 Dose Rationale

The dosing strategy in the Retreatment and Extension Periods will be based on the PK and serum bone turnover marker data from the Phase 2b ASTEROID study (completed) and data from the ongoing Phase 2/3 UX143-CL301 study (ages 5 to < 26 years). In the ASTEROID study, a setrusumab dose of 20 mg/kg QM increased DXA BMD, biomarkers of bone formation, and bone strength indices in adult patients with OI with an acceptable safety profile. An effect of body weight on setrusumab PK was observed, with setrusumab exposures decreasing as body weight decreased.

The dosing strategy for the Retreatment Period will also take into account data from the Phase 2 Period of the UX143-CL301 study (a seamless Phase 2/3 study with setrusumab in subjects with OI ages 5 to < 26 years). The Phase 2 Period of the UX143-CL301 study will evaluate the PK/pharmacodynamics (PD) of setrusumab at 2 dose levels, 20 and 40 mg/kg. PK/PD data from the Phase 2 Period of UX143-CL301 will be incorporated into a population PK/PD model developed using data from previous setrusumab studies, including ASTEROID, to inform the dose for the Phase 3 Period of UX143-CL301, as well as the dose for this study (UX143-CL203).

7.2. Duration

7.2.1. Duration of Subject Participation

Screening may take up to 1 month. The Observation Period is expected to take up to 18 months. The Retreatment Period is 12 months. The Extension Period continues until setrusumab is commercially available in a subject's given region.

7.2.2. End of Study Definition

The end of the study is defined as the date of safety follow-up for the last subject in the study.

7.3. Changes to the Protocol due to Covid-19

Changes to the protocol or Investigational Plan to minimize or eliminate immediate hazards or to protect the life and well-being of research subjects and/or study staff may be implemented without Institutional Review Board/Independent Ethics Committee (IRB/IEC) approval or before filing an amendment to the competent authority but are required to be reported afterward. Investigators should contact Ultragenyx or Designee to determine an appropriate course of action, which may include but is not limited to remote visits, home health visits, and out of window visits or assessments. Any changes to the protocol or investigational plan must be documented. The Investigator will work with Ultragenyx or Designee and IRB/IEC to prioritize reporting of protocol deviations that impact safety of trial subjects.

8. POPULATION

Prospective protocol deviations (ie, protocol waivers or exemptions) are not permitted.

8.1. Inclusion Criteria

Subjects who participated in ASTEROID were ages 19 to 74 years at the time of enrollment. Eligible individuals must meet all of the following criteria:

- 1. Males or females who participated in the Phase 2b ASTEROID study
- 2. Females of childbearing potential must consent to use highly effective contraception (Appendix 2) during the Observation, Retreatment, and Extension Periods through 2 months after the last dose of setrusumab and agree not to become pregnant. Provide informed consent after the nature of the study has been explained, and prior to any research-related procedures

8.2. Exclusion Criteria

Individuals who meet any of the following exclusion criteria will not be eligible to enroll in UX143-CL203:

- 1. Known hypersensitivity to setrusumab or its excipients that, in the judgment of the Investigator, places the subject at increased risk for adverse effects.
- 2. Presence or history of any condition that, in the view of the Investigator, would interfere with participation, pose undue risk, or would confound interpretation of results.
- 3. Pregnant or breastfeeding or planning to become pregnant (self or partner) at any time during the study
- 4. Willing to discontinue bisphosphonate use at least 3 months prior to the Retreatment Screening Visit (if applicable). Once enrolled in UX143-CL203, individuals who meet any of the following exclusion criteria will not be eligible to participate in the Retreatment Period:
- 5. Concurrent participation in any study that is examining the safety and efficacy of any investigational product or investigational medical device that alters bone health during the Retreatment and Extension Periods, per discretion of the Investigator in consultation with the Medical Monitor.
- 6. Presence or history of any condition that, in the view of the Investigator, would interfere with participation, pose undue risk, or would confound interpretation of results.
- 7. Calcium levels outside the normal range. If the subject's calcium level is not within the normal range, decision to retest should be made in conjunction with the Medical Monitor.
- 8. GFR ≤ 29 mL/min. If the subject's GFR is ≤ 29 mL/min, decision to retest should be made in conjunction with the Medical Monitor.
- 9. History of skeletal malignancies or bone metastases at any time
- 10. History of neural foraminal stenosis (except if due to scoliosis)

11. History of myocardial infarction, angina pectoris, ischemic stroke or transient ischemic attack

- a. Investigators should consider whether the potential benefits of treatment outweigh the potential risks in patients with other cardiovascular risk factors such as hypertension, hyperlipidemia, familial hyperlipidemia, family history of premature ischemic cardiovascular disease, smoking, diabetes mellitus, and metabolic syndrome. Suggested criteria and references for evaluation of risk factors will be provided in the Study Reference Manual.
- 12. History of or concomitant uncontrolled diseases such as hypo-/hyperparathyroidism, hypo-/hyperthyroidism, Paget's disease, abnormal thyroid function or thyroid disease or other endocrine disorders or conditions that could affect bone metabolism eg, Stage IV/V renal disease
- 13. A history of rickets or osteomalacia or any skeletal condition (other than OI) leading to long-bone deformities and/or increased risk of fractures
- 14. Documented alcohol and/or drug abuse within 12 months prior to dosing or evidence of such abuse as indicated by the laboratory results during the screening/baseline assessments
- 15. Documented history of significant psychiatric or medical disorder that would prevent the participant complying with the requirements of the protocol or would make it unsafe for the participant to participate in the study as judged by the investigator
- 16. Current/previously reported allergy to the study drug or any of its excipients or the class of drug under investigation
- 17. History of external radiation

8.3. Subject Discontinuation and Stopping Rule Criteria

8.3.1. Discontinuation of Intervention

If a subject is withdrawn from treatment due to safety reasons or if a subject has an ongoing SAE or AESI considered related to study drug at the end of participation, the subject should be followed until the event resolves, or the subject's condition has stabilized.

8.3.2. Discontinuation from Study

A participant may withdraw from the study at any time at his/her own request or may be withdrawn at any time at the discretion of the Investigator for safety, behavioral, or compliance reasons. Ultragenyx must be notified of all subject withdrawals as soon as possible. Ultragenyx also reserves the right to discontinue participation of an Investigator due to poor enrollment or noncompliance, as applicable.

In the event a subject discontinues treatment, he or she will remain in the study for safety monitoring purposes, unless continued participation in the study poses a risk to the subject as determined by the Investigator and/or Medical Monitor.

If a subject discontinues from the study prematurely, reasonable efforts should be made to perform the early termination (ET) Visit procedures within 2 weeks of discontinuation. A safety follow-up will be performed 2 months after the subject's last treatment. In the event a subject has an ET, all efforts will be made to monitor the subject through the end of the study.

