10. ASSESSMENTS

Assessments, including sample collection, and associated timing are provided in Table 3 and Table 4. Protocol waivers or exemptions are not allowed.

Data will continue to be collected for all endpoints on all subjects, including those who have discontinued study treatment but remain in the study. Site Investigators will be trained about the importance of subject retention and steps to prevent missing data. Reasons for missed assessments will be collected.

The completeness of the data affects the integrity and accuracy of the study analyses. Therefore, every effort will be made to ensure complete, accurate and timely data collection, and to avoid missing data.

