11. STATISTICAL CONSIDERATIONS

A full description of the analysis details will be provided in the Statistical Analysis Plan (SAP).

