11.1. Sample Size Determination

As only subjects who participated in the ASTEROID study are eligible, the sample size for this study is limited to the number of subjects who participated in ASTEROID and not driven by hypothesis testing. Assuming % recruitment failure rate from the ASTEROID study and % dropout rate by Month $1\overline{2}$ of the Retreatment Period, there will be around subjects with data at Month 12. For the primary endpoint of percentage change from Retreatment Baseline in lumbar spine BMD measured by DXA at Month 12 of the Retreatment Period, assuming the percentage change from Month 0 of the Retreatment Period (Retreatment Baseline) in lumbar spine BMD at Month 12 of CC , a sample size of around subjects will provide greater than work power to detect the change from baseline at 1-sided significance level of CC. For the secondary endpoint of percentage change from Retreatment Baseline in total hip BMD at Month 12 of the Retreatment Period, assuming the percentage change from Month 0 of the Retreatment Period (Retreatment Baseline) in total hip BMD at Month 12 of , a sample size of around currently subjects will provide greater than % power to detect the change from baseline at 1-sided significance level of Analysis Sets

For the purposes of analysis, the analysis sets are defined in the SAP.

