11.2.2. Efficacy Analyses

11.2.2.1. Primary and Secondary Efficacy Endpoints

The primary endpoint, percentage change from Retreatment Baseline in lumbar spine BMD measured by DXA at Month 12 of the Retreatment Period will be analyzed using a mixed-effects model for repeated measures that includes visit as a categorical variable and adjusted for baseline measurement. Other covariates may be considered. Model-based estimates of the percentage changes from baseline and corresponding of confidence intervals will be provided along with p-values.

The secondary endpoint, percentage change from Retreatment Baseline in total hip BMD measured by DXA at Month 12 of the Retreatment Period, will be analyzed similarly to lumbar spine BMD as described above.

The other secondary endpoint, number of fractures (total and by fracture type) and proportion of subjects who experience a fracture, as confirmed by radiograph during the Retreatment Period, will be summarized descriptively. The annualized new fracture rate during Retreatment Period will be compared with the annualized fracture rate during the Observational Period and\or Off-study Period using a generalized linear mixed effect model.

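### Does Section 8.3.2 let sites skip the Month 12 DXA in subjects who stop setrusumab, and so inflate the primary BMD estimate?

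*Combined protocol and SAP*

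**What the plan says.** Section 8.3.2 (Discontinuation from Study) says that a subject who stops treatment "he or she will remain in the study for safety monitoring purposes", unless staying would put the subject at risk. It names no other purpose and does not point to Section 10.

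Section 10 (Assessments) states: "Data will continue to be collected for all endpoints on all subjects, including those who have discontinued study treatment but remain in the study". It also rules out waivers, requires investigators to be trained on retention, and has the reasons for missed assessments recorded.

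Table 3 places DXA in the Retreatment Period at Months 0, 6 and 12. As far as the extracted table can be read, it makes no exception for subjects off treatment.

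Section 11.2.2.1 gives the primary endpoint as "percentage change from Retreatment Baseline in lumbar spine BMD measured by DXA at Month 12 of the Retreatment Period", which "will be analyzed using a mixed-effects model for repeated measures that includes visit as a categorical variable and adjusted for baseline measurement". It states no estimand, no rule for values obtained after treatment stops, and no missing-data sensitivity analysis. Sections 11, 11.1 and 11.2.1 leave the full analysis details and the analysis sets to the SAP. No SAP text is included in the document reviewed.

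On what happens off drug, Section 7.1.3 describes the earlier ASTEROID study, "with discontinuation of therapy resulting in partial loss of BMD gains over the next 12 months".

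**The concern.** The two sections give different reasons for keeping the same subjects. Coordinators who consult only Section 8.3.2 might treat a stopper as a safety follow-up case. A note to Table 3 allows visits without DXA or radiographs to be done at home, so such a subject might never be brought in for the Month 12 scan.

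That would reach the primary endpoint. There are only two DXA visits after Retreatment Baseline. A mixed model for repeated measures assumes that missing values are missing at random, so it predicts a stopper's Month 12 value from subjects with similar earlier BMD who were scanned, most of them still on drug. If BMD falls after stopping, that prediction is too high as a description of the subject's actual state. The Retreatment Period has a single arm, so no control group absorbs the error. At stake would be the size of the estimated gain and the coverage of its interval, not whether BMD rose.

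**Working it through.** **1. What a site must do.** The two sections set side by side:

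| Question | Section 8.3.2 | Section 10 and Table 3 |
|---|---|---|
| Does the stopper stay in the study? | Yes | Yes, presupposed |
| For what? | Safety monitoring | All endpoints |
| Is efficacy collection ended? | Not stated | No, expressly continued |
| Is the Month 12 DXA scheduled? | Silent | Yes, with no off-treatment exemption seen |

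Section 8.3.2 does not say that safety is the only purpose. Section 10 addresses data collection in exactly these subjects and is the more specific of the two. Both can be obeyed at once, and obeying both produces the scan. Omitting it would be a protocol deviation.

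**2. What the model does if scans are missing.** The protocol has no figure to reproduce, because the dropout rate, effect size and SD in Section 11.1 are redacted. All inputs below are therefore assumptions. Let d be the share of subjects who stop and have no Month 12 DXA, G the on-drug Month 12 gain, and L the fraction of that gain absent at Month 12 in stoppers. The expected excess over the actual Month 12 mean is

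bias = d × G × L.

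For L, assume on-drug gains of 4 to 5% at Month 6 and 6 to 8% at Month 12, with stopping just after Month 6. The later gain forgone is (6 − 4)/6 = 33% to (8 − 5)/8 = 38% of the Month 12 value. Also losing 10 to 50% of the Month 6 gain gives (2 + 0.4)/6 = 40% to (3 + 2.5)/8 = 69%, so L is taken as 40 to 70%.

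| Case | d | G | L | Bias (points) | Actual mean | Bias / actual mean |
|---|---|---|---|---|---|---|
| Low | 5% | 6% | 40% | 0.12 | 5.88% | 2% |
| Central | 10% | 8% | 55% | 0.44 | 7.56% | 6% |
| High | 20% | 8% | 70% | 1.12 | 6.88% | 16% |

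With an assumed N of 80, SDs of 5 and 7 and a correlation of 0.7, simulated 95% interval coverage was about 94%, 92% and 74% respectively. With the off-drug scans taken and used, bias was 0.0 and coverage about 95% in every scenario.

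A second simulation (N = 90, G of 5 or 10%, d of 5 to 20%, L of 25 to 100%, SDs 6 and 7, correlation 0.7) agreed. The model returned the on-drug mean each time. For G = 10%, d = 10% and L = 50% it gave 10.01% against an actual 9.51%. The mechanism is real if scans are missing.

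**3. How much of this the wording could cause.** The share d mixes two groups. Subjects who leave the study may lack the scan however Section 8.3.2 is worded. Only those who stop, stay in the study, and go unscanned because a site overlooked Section 10 belong to this point. If all of d stopped but stayed, and a fraction q of them were missed in that way, the central bias is q × 0.44 points: 0.44 if every site misreads, and zero if sites follow Section 10. The documents say nothing that sizes q.

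**4. Whether the conclusion could change.** The lowest actual mean over the assumed ranges is 6 − 0.20 × 6 × 0.70 = 5.16%. With SD 7 and N = 80 the standard error is 7/√80 = 0.78, so this lies 5.16/0.78 = 6.6 standard errors above zero.

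**5. Whether it is a bias at all.** That depends on the target. For the Month 12 mean regardless of stopping, the prediction is too high. For the mean had subjects stayed on drug, the same model aims at the intended quantity under missing at random. Tables 1 and 7 tie the primary endpoint to 12 months of drug, which fits the second target at least as well.

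**The case for a change.** The best case for acting is that sites, not statisticians, decide whether a scan is taken. Section 8.3.1, like 8.3.2, speaks only of following safety events, so neither discontinuation section mentions efficacy assessments. A scan never taken cannot be recovered by a later SAP. Because "the sample size for this study is limited to the number of subjects who participated in ASTEROID and not driven by hypothesis testing", the estimate itself is the main product, and a cross-reference would cost one sentence. Naming an estimand and adding a return-to-baseline sensitivity analysis would also cover subjects who leave the study.

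Part of this stands. The cross-reference would be tidier, and the model's behaviour with missing scans is as described. But the instruction is already in Section 10, so the sentence would clarify without changing what the plan requires.

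The argument for a regardless-of-stopping estimand is weaker than it looks. Section 7.1.3 says that retreatment "will provide insight into the effects of stopping and restarting treatment with setrusumab", but the context is stopping after ASTEROID and restarting here, with or without a bisphosphonate in between, not stopping midway through Retreatment. Choosing that estimand is a preference, not the correction of an error.

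A sensitivity analysis for study leavers is sensible, and a SAP is where it would normally appear. Its absence from a protocol summary does not show that it is absent from the plan. Section 8.3.2 also asks for every effort to monitor early terminators to the end of the study, so it cannot be taken as certain that they have no later data.

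**Conclusion.** No change to the plan is needed. Sections 8.3.2 and 10 are worded unevenly but do not conflict. Together with Table 3 they require the Month 12 DXA in subjects who stop setrusumab and stay in the study. The estimand, the handling of off-drug values and any missing-data sensitivity analysis are details that the protocol defers to the SAP. An analyst would be expected to settle them there, and the reviewed text cannot show that they were left out.

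The illustrative range of 0.12 to 1.12 percentage points rests wholly on assumed gain, share, loss, SDs, correlation and N. It combines study leavers with subjects affected by the wording. It fixes the stop just after Month 6, and later stops would contribute less. The protocol reports loss over 12 months off drug, without a figure and in a period when zoledronic acid was optional, so it does not support a specific six-month loss. Even at the unfavourable end of these assumptions, the finding of a BMD gain is unaffected.
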